3.4.2.2 Safety

The following safety data will be summarized using Clopper-Pearson method to estimate the 95% CI by age subgroup, intervention group and pooled age subgroups. The current Medical Dictionary for Regulatory Activities (MedDRA) version will be used for the coding of all AEs/reactions.

Solicited Reactions

Number and percentage of participants with:

- Presence of solicited injection site reactions and solicited systemic reactions occurring up to 7 days after injection
- Each solicited reaction according to time of onset, maximum intensity, and number of days of occurrence and action taken

Unsolicited Events and Reactions

Number and percentage of participants with:

- Any unsolicited immediate systemic event in the 30 minutes after injection according to System Organ Classes (SOC) and Preferred Terms (PT)
- Any unsolicited event and reaction 28 days after injection according to SOC and PT
- Any unsolicited event/reaction according to time of onset, maximum intensity, and duration

SAEs

Number and percentage of participants with:

• Any SAE within 28 days after injection and throughout the entire study according to SOC and PT, seriousness, and outcome

AESIs

Number and percentage of participants with:

• Any AESI within 28 days after injection and throughout the entire study according to SOC and PT, seriousness, and outcome

3.4.2.3 Complementary analysis

In addition, as a complementary analysis to support bridging discussion, Bayesian method will be used to evaluate the probability of non-inferiority in terms of GMTs for post-vaccination HAI Ab titer. The posterior probability of the true ratio of GMTs (RIV4/IIV4) to be higher than the commonly accepted non-inferiority margin (0.667) will be calculated using the Bayesian approach to support bridging with previous non-inferiority trials.

Further details about the statistical methodology are provided in the Appendix 2.

3.4.3 Handling of Missing Data and Outliers

3.4.3.1 Safety

Generally, no replacement will be done for safety missing data and outliers.

3.4.3.1.1 Immediate

For unsolicited systemic AEs, a missing response to the "Immediate" field is assumed to have occurred after the 30-minute surveillance period and will not be imputed.

3.4.3.1.2 Causal Relationship

By convention, all events reported at the injection site (either solicited or unsolicited) will be considered as related to the administered product and then referred to as reactions. In a same way, all solicited systemic events pre-listed in the CRF are also considered as related to vaccination and will be considered as reactions.

- For unsolicited systemic AE, missing relationship will be considered as related to study vaccine at the time of analysis.
- The missing relationship to study procedures for SAEs will not be imputed.

3.4.3.1.3 Intensity

For solicited reactions, missing intensities will be handled as described in Section 4.2.1.1.1. For unsolicited AEs, missing intensities will remain missing and will not be imputed.

3.4.3.1.4 Start Date and End Date

Missing or partially missing start dates or end dates for unsolicited AEs (including SAEs) will remain missing and not be imputed. If the start date is missing or partially missing, the time of onset will be considered to be missing. Nevertheless, unsolicited AEs with missing time of onset will be included in analyses. If either the start date or end date is missing or partially missing, the duration will be considered missing. Missing or partially missing end dates for ongoing solicited AEs will remain missing and not be imputed

3.4.3.1.5 Action Taken

Missing actions taken will remain missing and not be imputed.

3.4.3.2 Immunogenicity

No imputation of missing values and no search for outliers will be performed. Lower Limit Of Quantification [LLOQ] and Upper Limit Of Quantification [ULOQ] management will be performed as described in Section 4.2.3.1.

3.5 Interim Analyses

No interim analysis is planned for this study.

This study will not include an early safety data review. However, participant safety will be continuously monitored by the Sponsor's internal safety review committee which includes safety signal detection at any time during the study.

3.6 Data Monitoring Committee (DMC)

Not applicable.

4 Complementary Information on Assessment Methods

Study assessments and procedures are detailed in Section 8 of the protocol. This section focusses on complementary/additional information not detailed in the protocol.

4.1 Complementary Information for Endpoints Assessment Methods

Not applicable.

4.2 Complementary Information on Derived Endpoints: Calculation Methods

4.2.1 Safety

4.2.1.1 Solicited Reactions

4.2.1.1.1 Daily Intensity

All daily records for solicited reactions will be derived into daily intensity according to the following classification: None, Grade 1, Grade 2, Grade 3, or Missing (Unknown).

For the derivation of daily intensities, the following sequential steps will be applied:

1) Solicited reactions (except Fever/Pyrexia) with CRF presence recorded as "No" and with all daily records missing (Unknown) then all daily intensities will be derived as None.

2) For non-measurable solicited reactions, daily intensities will correspond to daily records reported in the clinical database. For measurable solicited reactions the daily measurements reported in the clinical database will be converted based upon the intensity scales defined in the protocol; this assumes a reaction that is too large to measure (non-measurable, "NM") is Grade 3. Note the intensity could be considered "None" (not a reaction) in the analysis despite being considered a reaction by the investigator (e.g., swelling measurement > 0 mm but < 25 mm in adults).

Note: The maximum intensity on the ongoing period is derived from the record of the maximum intensity/measurement after the end of the solicited period following the rule described above.

4.2.1.1.2 Maximum Intensity

Maximum overall intensity is derived from the daily intensities computed as described in Section 4.2.1.1.1 and is calculated as the maximum of the daily intensities over the period considered.

4.2.1.1.3 Presence

Presence is derived from the maximum overall intensity over the time period considered:

- None: No presence
- Grade 1, Grade 2, or Grade 3: Presence
- Missing or Unknown: Missing presence

Participants with at least one non-missing presence for a specific endpoint will be included in the analysis. Conversely, those without a non-missing presence will not be included in the analysis of the endpoint.

4.2.1.1.4 Time of Onset

Time of onset is derived from the daily intensities computed as described in Section 4.2.1.1.1. It corresponds to the first day with intensity of Grade 1, Grade 2, or Grade 3.

Note: If a reaction is not continuous (i.e., reaction occurs over two separate periods of time intervened by at least one daily intensity Missing or None) then the time of onset is the first day of the first occurrence.

Time of onset period is displayed as D1-D4, D5-D8.

4.2.1.1.5 Number of Days of Occurrence During the Solicited Period

Number of days of occurrence over the period considered is derived from the daily intensities computed as described in Section 4.2.1.1.1. It corresponds to the number of days with daily intensities of Grade 1, Grade 2, or Grade 3. Number of days of presence on the solicited period with a specified intensity may also be derived.

The number of days of occurrence during the solicited period is displayed as 1-3 days, 4-7 days and 8 days.

4.2.1.1.6 Overall Number of Days of Occurrence

If a reaction is ongoing at the end of the solicited period, then the overall number of days of presence is derived from the daily intensities and the end date of the reaction after the end of the solicited period.

The overall number of days of occurrence is:

(End date - vaccination date) + (number of days of occurrence within the solicited period) -

length of the solicited period + 1

If the end date is missing or incomplete (contains missing data), the overall number of days of presence will be considered as Missing.

The overall number of days of occurrence is displayed as 1-3 days, 4-7 days, 8 days or more and Missing.

4.2.1.1.7 Ongoing

Ongoing is derived from the last daily intensity of the solicited period computed as described in Section 4.2.1.1.1 and the maximum intensity on the ongoing period. The investigator's ongoing flag is not used because the measurement would determine the ongoing status of the reaction.

- Ongoing: if the last daily intensity of the solicited period is at least Grade 1 and the maximum intensity on the ongoing period is at least Grade 1
 - Not ongoing: if the last daily intensity of the solicited period is None or the maximum intensity on the ongoing period is None.
- Missing: all other conditions (in this case, it is not included in the denominator of the ongoing analysis in the safety tables).

4.2.1.2 Unsolicited AEs

4.2.1.2.1 **Presence**

An observation will be considered an event if it has at least a verbatim term and the intensity is not None.

Events for which the intensity is None are not included in safety analysis but are included in separate listings.

4.2.1.2.2 Intensity

Intensity will be derived according to the following classification: None, Grade 1, Grade 2, Grade 3, or Missing.

If the unsolicited AE is measurable and its preferred term is part of the list of solicited reactions, then the measurement is derived based upon and following the same rule of the intensity scales defined in the protocol for that measurable injection site or systemic reaction. Note the intensity could be considered as "None" (not a reaction) in the analysis despite being considered a reaction by the investigator (e.g., swelling measurement >0 mm but < 25 mm in adults).

Intensity for the other unsolicited AEs will correspond to the value reported in the CRF.

The maximum intensity corresponds to the highest intensity for a unique term.

4.2.1.2.3 Time of Onset

Time of onset is derived from the start date of the unsolicited AE and the date of vaccination:

Time of Onset = start date of the unsolicited AE - date of vaccination before the unsolicited AE + 1.

The time of onset is considered as missing only if one or both dates are missing or partially missing.

The unsolicited AEs will be analyzed "Within 28 days" after vaccination, which corresponds to AEs with a time of onset between 1 and 29 days or missing. An AE with missing time of onset will be considered to have occurred just after the vaccination, so will be included in these tables.

Time of onset period is displayed as D1-D4, D5-D8, D9-D15, D16 or later, and Missing.

Note: To further clarify the analysis,

- Any SAEs or AESIs collected throughout the study with time of onset > D29 after vaccination will not be presented in tables of unsolicited AEs within 28 days but only in tables of SAEs or AESIs.
- Any unsolicited AEs (planned to report up to 28 days) with time of onset between D01 and D29 or missing after vaccination will be presented in the tables of unsolicited AEs within 28 days.
- Any unsolicited AEs (planned to report up to 28 days) with time of onset > D29 after vaccination will not be presented in any tables but listed separately.
- Any unsolicited AEs with null (0) or negative time of onset will be excluded from the above tables and listed separately.

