4.2.1.2.5 Serious Adverse Events

An event will be considered as a serious event if "Yes" is checked for "Serious" in the CRF.

SAEs will be analyzed using the following periods:

- Within 28 days after vaccination
- During the study (i.e., all SAEs occurred during the study)

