4.2.1.2.6 Adverse Events of Special Interest

An event will be considered as an AESI if "Yes' is checked for "Is the event an AESI?" in the CRF.

AESIs will be analyzed using the same time periods as SAEs described in Section 4.2.1.2.5:

- Within 28 days after vaccination
- During the study (i.e., all AESIs occurred during the study)

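### An SAE or AESI with only a month and year for its start is counted within 28 days, even when that month lies wholly after D29

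*SAP*

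**What the plan says.** SAP 3.4.3.1.4 covers SAEs by name: "Missing or partially missing start dates or end dates for unsolicited AEs (including SAEs) will remain missing and not be imputed". It continues: "If the start date is missing or partially missing, the time of onset will be considered to be missing".

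SAP 4.2.1.2.3 repeats that rule. It defines the 28-day period for unsolicited AEs as an onset of 1 to 29 days or missing, and adds: "An AE with missing time of onset will be considered to have occurred just after the vaccination, so will be included in these tables". Two clarifying bullets follow:

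- The first removes late serious events from the 28-day unsolicited-AE tables: "Any SAEs or AESIs collected throughout the study with time of onset > D29 after vaccination will not be presented in tables" of that kind, and they appear only in the SAE or AESI tables.
- The second keeps in the 28-day tables "Any unsolicited AEs (planned to report up to 28 days) with time of onset between D01 and D29 or missing".

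SAP 3.4.2.2 plans a summary of "Any SAE within 28 days after injection and throughout the entire study according to SOC and PT, seriousness, and outcome", with a parallel line for AESIs. SAP 4.2.1.2.5 names the first SAE period as "Within 28 days after vaccination", and 4.2.1.2.6 says "AESIs will be analyzed using the same time periods as SAEs described in Section 4.2.1.2.5". Neither section has a date rule of its own.

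Protocol 8.3.1 collects SAEs and AESIs from D01 to D181, and non-serious unsolicited AEs only from D01 to D29. Protocol 10.3.1 counts SAEs among unsolicited AEs.

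**The concern.** Treating a missing onset as early suits non-serious AEs. They are collected only to D29, so an undated one very probably belongs there, and that use is not questioned.

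SAEs and AESIs are followed for about five months beyond D29. For them a partial date often carries enough information to settle the window, and the SAP discards it. An event recorded with a month and year that exclude D01 to D29 is still treated as if it began just after vaccination.

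At stake is the accuracy of the 28-day SAE and AESI counts. These are read for closeness in time to vaccination, and a single event is visible in them. Because SAEs are unsolicited AEs, the same event could also enter the 28-day unsolicited-AE tables. The whole-study SAE and AESI tables, which match the primary endpoint of presence throughout the trial, do not depend on the window.

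**Working it through.** **The stated window.** SAP 4.2.1.2.3 gives onset = start date − vaccination date + 1. An event 28 days after vaccination has onset 28 + 1 = 29, so the stated range of 1 to 29 reproduces.

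**The path of a month-only SAE through the rules**

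1. The start date is partial, so onset is missing (3.4.3.1.4, repeated in 4.2.1.2.3).
2. The exclusion for onset after D29 needs a numerical onset, so it does not apply.
3. Missing onset counts as within 28 days (4.2.1.2.3, the only definition of that period in the SAP).
4. Sections 4.2.1.2.5 and 4.2.1.2.6 do not override step 3.

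**Dated example.** Vaccination is assumed on 15 October 2021, so D29 is 12 November 2021 and D181 is 13 April 2022.

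| Recorded start | Possible onset | Under the current rule | Using the recorded month |
|---|---|---|---|
| November 2021 | D18 to D47 | within 28 days | ambiguous; stays within 28 days |
| December 2021 | D48 to D78 | within 28 days | whole-study tables only |
| February 2022 | D110 to D137 | within 28 days | whole-study tables only |

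**Share of the collection period exposed (illustration only).** Assume onset is uniform over D01 to D181, with month and year known and the day missing.

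- Days after D29: (181 − 29)/181 = 152/181 = 84.0%.
- Days in a calendar month wholly after D29, with the vaccination date varied over 365 calendar days: 122/181 to 152/181, or 67.4% to 84.0%, mean 75.8%. Limiting vaccination dates to 1 September 2021 to 28 February 2022 gives the same range and mean.
- Days after D29 but in the month that contains D29: 0 to 30 of 181 (0 to 16.6%), mean 14.7 days. These cannot be resolved from the month and would stay under the current rule.

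These are shares of calendar days, not a forecast of misplaced events.

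**Effect of one misplaced event.** SAP 3.2 plans 75 participants per age-by-vaccine cell, hence 75 + 75 = 150 per vaccine. Intervals are Clopper-Pearson 95%, as in the SAP.

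| Denominator | No event | One misplaced event |
|---|---|---|
| 75 | 0% (0 to 4.80%) | 1/75 = 1.3% (0.034 to 7.21%) |
| 150 | 0% (0 to 2.43%) | 1/150 = 0.7% (0.017 to 3.66%) |

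**The case against.** The strongest counter-argument is textual. The second clarifying bullet attaches the words on missing onset only to AEs planned to be reported up to 28 days, and the note separates the unsolicited-AE tables from the SAE and AESI tables. On that reading the SAP does not misplace these events; it is silent on them. This does not remove the problem. The sentence on missing onset refers to any AE, 3.4.3.1.4 names SAEs, the protocol counts SAEs as unsolicited AEs, and no other rule places an SAE or AESI with missing onset. If the narrower reading were adopted, a rule would still have to be written.

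The second argument is that the convention is conservative, identical in both arms and visible, because the onset display has a missing category. That is a fair defence when timing is unknown. It is weaker when the recorded month shows the event was late, and in a two-arm description an event wrongly moved early in the IIV4 arm does not make the comparison cautious.

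The third argument is rarity, and it largely stands. SAEs and AESIs are reported within 24 hours, the investigator reviews medical records, a memory aid covers the time after Visit 2, and source data are verified. The documents do not show how the CRF stores partial dates, so a known month with a missing day is an assumption. Against this, the only planned contact after Visit 2 is the telephone call at D181, and the SAP itself provides for partial dates.

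It is also true that the study is descriptive, that no decision rule uses the 28-day SAE rate, and that the 0/75 to 1/75 change is what any single event would do to a cell that size.

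**Conclusion.** The concern holds and is minor. On the natural reading of the SAP, an SAE or AESI with a partial start date goes into the 28-day tables even when its recorded month and year exclude D01 to D29. The number of such events is unknown and may be zero; each would add about 1.3 percentage points to a cell of 75 or 0.7 to a vaccine group of 150.

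The conclusion assumes that the general sentence on missing onset governs SAEs and AESIs, and that partial dates can retain month and year. Confidence is medium because of the narrower wording in the clarifying bullet. The example rests on an assumed vaccination date, and the 67% to 84% range on uniform onset.

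**What to change.** Add to SAP 3.4.3.1.4 and 4.2.1.2.3, for SAEs and AESIs only: when the start date is partial, the known month and year are compared with the vaccination date; if every compatible date is after D29, the event appears only in the whole-study SAE and AESI tables. Keep the current rule for wholly missing dates and for partial dates compatible with D01 to D29. No full date imputation is needed, and non-serious AEs are unchanged. A cross-reference from 4.2.1.2.5 and 4.2.1.2.6 would help the programmer but is not essential.

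The cost is one sentence in the SAP and a small change to the derivation of the 28-day flag. No new data are required.

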4.2.1.2.4 Duration

Duration is derived from the start and end dates of the unsolicited AE:

```
Duration = End date of unsolicited AE - start date of unsolicited AE + 1.
```

The duration is considered as missing only if one or both of the start and end dates of the unsolicited AE is missing or partially missing.

Duration will be displayed by period as 1-3 days, 4-7 days, 8 days or more and Missing.

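### The SAP duration rule files ongoing events as Missing even when the record already shows that they lasted 8 days or more

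*SAP*

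**What the plan says.** SAP 3.4.2.2 plans to tabulate "Any unsolicited event/reaction according to time of onset, maximum intensity, and duration". SAP 4.2.1.2.4 gives the formula "Duration = End date of unsolicited AE - start date of unsolicited AE + 1" and the display: "Duration will be displayed by period as 1-3 days, 4-7 days, 8 days or more and Missing".

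The handling of absent dates is stated three times:
- SAP 4.2.1.2.4, unsolicited AEs: "The duration is considered as missing only if one or both of the start and end dates of the unsolicited AE is missing", and the sentence goes on to include partial dates.
- SAP 3.4.3.1.4, unsolicited AEs including serious ones: "If either the start date or end date is missing or partially missing, the duration will be considered missing". For solicited reactions it adds: "Missing or partially missing end dates for ongoing solicited AEs will remain missing and not be imputed".
- SAP 4.2.1.1.6, solicited reactions: "If the end date is missing or incomplete (contains missing data), the overall number of days of presence will be considered as Missing". The display there is: "The overall number of days of occurrence is displayed as 1-3 days, 4-7 days, 8 days or more and Missing".

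None of these sections makes an exception for an event recorded as ongoing. None has a lower-bound rule or an ongoing row in the duration display.

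**The concern.** An unresolved event has no end date because it has persisted, so here the missingness is produced by the quantity being described. The top class has no upper limit, so the start date and the last date on which the event was known to be present can be enough to place it. The SAP discards that information. Events already known to be long leave the row where a reader would look for them and join events whose dates are simply unknown. The error goes one way: the count of long events can only be too low.

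What is at stake is the description of how long AEs last, which is part of the safety description in SAP 3.4.2.2. No immunogenicity result, AE incidence or sample-size figure depends on it.

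**Working it through.** The plan states no figure for durations, so there is none to reproduce. The check applies the SAP's own formulas to events whose persistence is on record.

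**Inputs.** Unsolicited non-serious AEs are collected from D01 to D29, and solicited reactions from D01 to D08, a period of 8 days (protocol 8.3.1). Visit 2 is on D29 with a window of +7 days, so D29 to D36 (protocol Table 1.1).

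**Unsolicited AEs.** For onset on day s and presence at a visit on day V, minimum duration = V − s + 1.
- V = 29: s = 1 gives 29; s = 5 gives 25; s = 15 gives 15; s = 22 gives 8; s = 23 gives 7. Every onset on D01 to D22 is already in the top class; D23 to D29 is not yet provable.
- V = 36: s = 29 gives 8, so every onset on D01 to D29 is in the top class.
- Serious AE with onset on D29, ongoing at the D181 call: 181 − 29 + 1 = 153 days.

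Without a complete end date, all of these are Missing under the current text. So is an event whose partial end date (month known, day not) lies wholly beyond its eighth day.

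**Solicited reactions.** With k days of occurrence within D01 to D08, overall days = (end date − vaccination date) + k − 8 + 1. If the reaction is ongoing past D08, the earliest possible end is D09, giving 8 + k − 8 + 1 = k + 1. So k = 7 gives at least 8 and k = 8 at least 9, both tabulated as Missing in the overall display. With k ≤ 6 the class is not provable.

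**Which events can stay without an end date.** Protocol 8.3.3 requires follow-up until resolution, stability or chronicity only for AEs that are related or caused discontinuation. Protocol 8.3 adds serious AEs to the investigator's follow-up duty. The 6-month call asks about serious AEs and AEs of special interest (protocol 8.3.2). An unrelated, non-serious AE that is ongoing at Visit 2 therefore has no required route to an end date. A related AE that becomes chronic may have none either.

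**Illustrative size for unsolicited AEs.** Assumptions, none from the documents: onset uniform over D01 to D29; duration T exponential or lognormal (log-SD 0.9), rounded up to whole days; no end date updated after Visit 2. The share of true 8-day-plus events that are Missing but provable is the average over s of P(T > V − s + 1), counting only s with V − s + 1 ≥ 8, divided by P(T > 7).

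Example, exponential with median 7 and V = 29: P(T > d) = r^d with r = 2^(−1/7) = 0.9057. The sum for d = 8 to 29 is (r^8 − r^30)/(1 − r) = (0.4529 − 0.0513)/0.0943 = 4.26. Then 4.26/29/0.5 = 0.29.

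| Duration model | Visit 2 on D29 | Visit 2 on D36 |
|---|---|---|
| Exponential, median 5 | 22% | 23% |
| Exponential, median 7 | 29% | 31% |
| Lognormal, median 5 | 22% | 23% |
| Lognormal, median 7 | 27% | 29% |

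At a D29 visit a further 7/29 = 24% of true 8-day-plus events start on D23 to D29. They are also Missing but cannot yet be proved to last 8 days. Adding them gives a total shortfall of 46% to 53%, but a minimum-duration rule cannot recover that 24%.

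If every AE's end date were updated up to D181, the shortfall would be about 2.5% even with a median of 30 days (exponential).

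**The case against.** The strongest reply is that the events that matter most for comparing vaccines are the ones least exposed. Solicited reactions and all injection-site events count as related by convention (protocol 10.3.3). Related AEs are followed until they resolve, stabilise or become chronic, and the investigator reports the date of disappearance or of chronicity (protocol 8.3.3, 10.3.3). New information goes into the original CRF record. This stands. It confines the gap mainly to unrelated, non-serious unsolicited AEs, plus related events that become chronic or stay unresolved.

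Second, solicited reactions have other displays. SAP 4.2.1.1.5 tabulates days within the solicited period with its own row for 8 days and needs no end date. SAP 4.2.1.1.7 derives ongoing status for a separate analysis. This also stands, so the overall-days display loses little that is not shown elsewhere.

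Third, Missing is a displayed row and the events still count in the other AE tables. That is true, but the row does not separate a known persistent event from an unknown date.

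Fourth, protocol 9.4.1 and SAP 3.4.1 rule out replacement of missing safety data. Assigning an open-ended class from recorded dates and status replaces no date, so that rule is not breached.

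Two stronger readings are tempting. A reader might infer that the comparison of RIV4 with IIV4 is pulled toward no difference. The documents do not support this, because vaccine-related events are the ones with mandated follow-up. A reader might also infer that the top row is understated by about half. That figure assumes that no AE, related or not, has its end date updated after Visit 2, which runs against protocol 8.3.3, and it includes events that no rule could classify at that visit.

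**Conclusion.** The point holds in a limited form. As written, the SAP classes as Missing any event without a complete end date, including events that recorded dates and status already place at 8 days or more. The clearest case is an unsolicited AE with onset on D01 to D22 still ongoing at a D29 Visit 2. The top row is understated, and long events with complete end dates remain correctly counted.

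The size cannot be derived from the documents. The illustrative 22% to 31% rests on the assumed duration distribution, on uniform onset, and above all on no end-date update after Visit 2; later updates would make it far smaller. The consequence is confined to descriptive safety-duration tables. The correction is still worth making because the error has a known direction and the remedy is short.

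**What to change.** In SAP 4.2.1.2.4, cross-referenced in 3.4.3.1.4 and applied likewise in 4.2.1.1.6, add a minimum-duration rule:
- Apply it when the start date is known and either the event is recorded as ongoing at Visit 2 or last contact, or a partial end date already implies at least 8 days.
- Compute the minimum duration from the last date the event is documented as present, or from the earliest date compatible with the partial end date. For solicited reactions use k + 1 when the reaction is ongoing past D08.
- If the minimum reaches 8 days, assign the top class. If not, show an ongoing event in a row for events ongoing at last contact, separate from a row for end date unknown.
- State that no date is imputed.

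The cost is SAP wording and a short derivation. Some durations will be classed from a lower bound rather than an exact value. The CRF is not among the documents, so the sponsor should first confirm that ongoing status and the date of last contact are available for unsolicited AEs.
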